5.3.5 Visit window

All visits during neoadjuvant therapy were to be within the range of -3 to +7 days of the planned date, and postoperative visits were considered to be 14 days, unless otherwise noted. Evaluations scheduled for the day of study treatment dosing (Day 1) per cycle should be completed prior to study treatment infusion/dosing, unless otherwise noted. Laboratory and imaging results should be reviewed prior to dosing. Scheduling a study visit at a protocol-specified time point that is in conflict with a holiday, weekend, or other event/law will allow the visit to be scheduled to the nearest feasible date.

Visit schedule

	sift	Treatment period (one cycle every 21 days)				Drug safety follow-up r	operation		Postoperative follow-up				
		Cycle 1	Cycle 2	Cycle 3	Cycle 4		Preoperative evaluation	Radical resection	1 week	1 month	3 months (EOT)	6, 12, 18, 24 months	9, 15, 21 months
fate (window)	-28 to -1	one	-3 to +7	-3 to +7	-3 to +7	28 after last dose (-3 to +7)	-7 to 0	28 – 42 after the last dose	±3	±7	±14	±14	±14
Informed consent a	X												
Demographic data/ Treatment historyb	X												
Physical examination/vital signs c	X	X	X	X	X	X	X		X	X	X	X	
ECOG assessment	X	X	X	X	X	X	X		X	X	X	X	
Surgical fitness evaluation	X						X						
Electrocardiogram d	X	X	X	X	X	X	X		X	X	X		
Hematology e	X	X	X	X	X	X	X		X	X	X	X	
Serum biochemistry e	X	X	X	X	X	X	X		X	X	X	X	
Urinalysis e	X	X	X	X	X	X	X		X	X	X	X	
Fecal analysise	X			X			X						

Coagulation e	X						X						
Pregnancy testf	X					X	X						
Hepatitis b two half qualitative g	X						X						
Hepatitis c qualitative g	X						X						
Venereal disease (HIV)g	X						X						
Marker screening (HER2 IHC)	X												
Thyroid functionh	X						X						
Chest CT plain scan i	X			X		X	X				X	X	
Total abdominal+pelvic CT plain scan+enhanced i	X			X		X	X				X	X	
Bladder (or pelvis) Multiparameter mri	X			X			X						
Bone scan i	X												
Previous/concomitant medications	X	X	X	X	X	X	X	X	X	X			
Adverse eventj	X	X	X	X	X	X	X	X	X	X	X		
Vidicon monoclonal antibody administration k		X	X	X	X								
Ampley monoclonal antibody administration l		X	X	X	X								
Radical resection and pathological evaluation m								X					
Archived/fresh tumor histon	X							X					
EQ-5D-5L/ EORTC QLQ-C30 o	X	X	X	X	X	X	X	X	X	X	X	X	
Living condition	X	X	X	X	X	X	X	X	X	X	X	X	X

Abbreviations: ECOG, Eastern Cooperative Oncology Group; CT: electronic computed tomography; MRI: magnetic resonance imaging; RECIST, evaluation criteria for efficacy of solid tumors; V, version; CTCAE: general term evaluation criteria for adverse events; EOT: end of treatment visit.

A. Written informed consent is required prior to any study-specific inspections or procedures. Standard treatment tests or workups performed prior to informed consent and within 28 days prior to enrollment that are available for screening evaluation do not need to be repeated unless otherwise specified.

B. including year of birth (or age), gender and race/ethnicity; Treatment history initially diagnosed, including prior medical therapy, local therapy, and surgical treatment. Information regarding imaging studies conducted prior to enrollment in the study may be collected for review by the investigator.

C Vital signs collected during the study included temperature, pulse, and blood pressure (systolic and diastolic) when the patient was at rest and at rest after 10 minutes. The patient's vital signs were recorded during the first 1 hour before, during, and 1 hour after the last two infusions of vidicon. For subsequent infusions, vital signs will be collected within 60 minutes prior to infusion and, if clinically indicated, during and 30 minutes after infusion. Patients should be asked by the investigator at each of the planned study visits during the treatment with vidicon for changes in vision, visual impairment, or ocular inflammation. Any change in vision should be referred to the appropriate specialist for further management guidance.

D. The patient should rest quietly for at least 10 minutes before undergoing ECG examination. If the ECG has significant clinical significance, color Doppler ultrasound (LVEF) will be added for investigation, and such symptoms as precordial pain and palpitation will appear, together with myocardial enzyme spectrum.

E Hematology (routine blood and coagulation tests), serum biochemistry (including cardiac, hepatic, and renal function tests), urinalysis and fecal analysis will be evaluated in the local laboratory. Results should be viewed within 24 hours prior to each dose of study drug after the end of Cycle 1. Fecal analysis is required if clinically indicated during the follow-up period.

F. A urine pregnancy test will be performed on all fertile females. A weakly positive urine pregnancy test must be confirmed by an additional serum pregnancy test.

G serological tests including HBV/HCV/HIV (HBV halves, HCV antibodies, HIV antibodies) will be performed in the local laboratory. HBV DNA testing needs to be added if HbsAg is positive. Additional HCV RNA testing is required if HCV antibodies are positive.

H. In addition to the screening period and preoperative evaluation, the investigator determines whether a thyroid function test is required if clinically indicated.

I. Imaging examinations have been taken under standard treatment before obtaining the written informed consent, and the collection

time is within 28 days before inclusion. If the results meet the clinical requirements and are qualified, no repeated examination is required, but the multi-parameter MRI of bladder (pelvis) after TURBT must be guaranteed. All measurable and evaluable lesions need to be evaluated and documented at the screening visit. Chest, abdomen and pelvis-containing plain CT scan (enhancement at the discretion of the investigator if necessary) and multi-parameter MRI of bladder (pelvis) were selected for imaging examination (VI-RADS score was conducted when conditions were ripe). For each patient, the same imaging studies were used as far as possible throughout the study. The investigator must review the imaging results prior to the next cycle of dosing. During the follow-up period, imaging examinations were selected according to the pathological response of the patient or local medical guidelines. During the follow-up period, if imaging recurrence or metastasis occurs, no imaging examination will be conducted during the follow-up period covered by this study. Craniocerebral examinations and bone scans are required when symptoms appear, if clinically indicated.

J. AEs and laboratory abnormalities will be graded according to NCI-CT Cae Version 5.0 (drugs), and CLAVIEN-DINDO (surgery), and all AEs will be evaluated for severity. Only SAEs should be reported after informed consent has been signed but prior to initiation of study drug administration. After initiation of study drug, all AEs and SAEs, regardless of relationship of study drug and procedure, will be evaluated and documented until 28 days after the last dose (including chemotherapy) or initiation of new anticancer therapy (whichever occurs first). Assessment and documentation of surgery-related adverse events should be performed within 90 days after surgery.

K. VDT will be administered intravenously every 3 weeks. The infusion time for the first infusion (Cycle 1, Day 1) should be not less than 60 minutes; If well tolerated, subsequent infusions should take no less than 30 minutes, the shortest time allowed for an infusion. Patients must be monitored for at least 60 minutes in an area equipped with resuscitation equipment and emergency medications following the infusion of vidicon on the first day of Cycles 1 and 2. Beginning with cycle 3, a minimum of 30 minutes of monitoring is required in areas equipped with resuscitation equipment and emergency medications. VID should not be coadministered with any other drugs. At each cycle, vidicon will be administered prior to PD-1 drug administration.

L. PyAmpley monoclonal antibody will be administered intravenously every 3 weeks. Administration of the drug was on the same day as that of the vidicon.

M. After radical surgery, the pathological staging after neoadjuvant therapy will be evaluated by the investigator based on the pathological results of surgical samples.

N. During the screening stage, patients must provide tumor tissue samples of TURBT and relevant pathological report at the same time, and can choose to send fresh surgical tissue or pathological white sheet for biomarker analysis. Fresh tumor samples also need to be collected during radical surgery. Patients with disease progression will be asked if an optional biopsy has been performed (see central laboratory sample management manual).

O. Patients were required to complete the EQ-5D-5L and EORTC QLQ-C30 questionnaires (Appendix 11, 12). Where feasible, patients are required to complete questionnaires prior to administration of study drug or any other procedure.

Q. Drug safety follow-up should be performed 28 days after the last dose of vidicon or Ampley monoclonal antibody (-3 to +7 days) and prior to initiating radical surgery, or prior to initiating new anti-cancer therapy, whichever occurs first. This visit can be combined with other visits as long as the drug safety visit occurs 28 days (-3 to +7 days) after the last dose. If routine laboratory tests (eg, hematology, serum biochemistry) were performed within 7 days prior to the drug safety visit, there is no need to repeat the same test. Imaging is not required at the drug safety follow-up if it is less than 28 days from the last imaging.

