5.2 Treatment

After completing all screening activities, patients confirmed to be eligible will enter the study and receive the following treatments and visits: new adjuvant treatment with vidicon combined with piAmpley monoclonal antibody (up to 4 dosing cycles), once every 3 weeks; The patient underwent radical cystectomy after neoadjuvant chemotherapy; The patient's complete pathological response rate, phase reduction rate, and regular follow-up of two years were detected postoperatively to evaluate the patient's drug/surgical safety and to evaluate the survival of the patient's radical resection after neoadjuvant immunization combined with chemotherapy.

New adjuvant regimens (up to 4 cycles administered): 2.0mg/kg, Vidisituzumab on Day 1, administered intravenously, Ampley monoclonal, 200mg, administered intravenously on Day 1 of each 21-day cycle. Order of use: Vidicidone monoclonal antibody → PyAmpley monoclonal antibody.

Surgical scheme: radical cystectomy+urinary diversion.

Specific treatment and visit designs are as follows.

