5.2.2 Drug treatment period

Upon completion of all screening activities, patients confirmed to be eligible will enter the study and receive treatment as follows: up to 4 cycles of administration of vidicon in combination with Ampley monoclonal antibody).

Imaging evaluation will be performed before the start of cycle 3 of new adjuvant therapy, and if the patient does not develop PD, treatment will be continued as planned; If the patient had PD, subsequent treatment would be administered at the discretion of the investigator.

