5.2.4 Surgical treatment

Preoperative evaluation will be performed prior to radical surgery, and if the patient meets the surgical indications, the investigator will perform radical cystectomy at an appropriate time as planned; If the patient is not suitable for surgery, the investigator decides to administer subsequent treatment. Disease progression occurs during the neoadjuvant treatment phase, or the AE fails to complete 4 cycles of neoadjuvant treatment (total neoadjuvant treatment duration does not exceed 15 weeks), but if the investigator assesses that the indication for radical surgery is met, surgery will be continued within the specified time frame and will still be considered eligible for treatment and evaluation for all study requirements. If the investigator determines that physical conditions preclude radical surgery, study treatment will be discontinued, an end-of-treatment visit will be given, and additional treatment selected by the investigator will be continued. If any of the conditions exceed the above time limits, but the investigator determines that the procedure is still acceptable, the team

leader unit will be contacted to determine whether or not they are eligible for study analysis. Patients who discontinue neoadjuvant therapy early due to disease progression or an intolerable adverse event (AE) before surgery and do not undergo surgery are given an end-of-treatment visit and will continue to receive other treatments selected by the investigator.

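### Visit-schedule footnote C ties the closer infusion vital signs to the last two infusions and then sets a rule for later ones that cannot exist; the first two are probably meant

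*Protocol*

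**What the plan says.** Footnote C to the visit schedule in Protocol section 5.3.5 has two consecutive sentences on vital signs around the disitamab vedotin infusion. The first sets the closer rule: "vital signs were recorded during the first 1 hour before, during, and 1 hour after the last two infusions of vidicon". The second sets the lighter rule: "For subsequent infusions, vital signs will be collected within 60 minutes prior to infusion and, if clinically indicated, during and 30 minutes after infusion".

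The number of infusions is capped but not fixed. Section 5.2 describes treatment as "up to 4 dosing cycles), once every 3 weeks". Section 5.2.2 places a decision point in the middle of treatment: "Imaging evaluation will be performed before the start of cycle 3 of new adjuvant therapy, and if the patient does not develop PD", treatment goes on as planned; otherwise the investigator decides what follows. Section 5.2.4 provides for "Patients who discontinue neoadjuvant therapy early due to disease progression or an intolerable adverse event (AE) before surgery".

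Footnote K to the same schedule governs observation after the same infusions. It says: "Patients must be monitored for at least 60 minutes in an area equipped with resuscitation equipment and emergency medications following the infusion of vidicon". It limits this to the period "following the infusion of vidicon on the first day of Cycles 1 and 2", and continues: "Beginning with cycle 3, a minimum of 30 minutes of monitoring is required".

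**The concern.** The second sentence of footnote C presupposes infusions that come after those named in the first. If the first names the last two, there are none, so one of the sentences must be wrong.

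This is an operative safety instruction, to be applied at the five centres listed in the protocol summary. Followed to the letter, it puts the mandatory readings during and 1 hour after infusion at the end of treatment and drops them at the first exposures. Sites could also reasonably read it in different ways. A patient who stops unexpectedly after Cycle 1 or 2 could be found, after the event, to have missed readings that nobody knew were due.

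**Working it through.** The protocol states no figure on this point, so there is none to reproduce. The check is a count over the possible numbers of cycles, followed by a comparison of footnotes C and K.

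**Inputs.** One infusion per 21-day cycle and at most four cycles (sections 5.2 and 5.2.2). Let *k* be the number of cycles a patient actually receives, *k* = 1 to 4.

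**Step 1: which infusions each wording covers.** The last two are cycles max(1, *k* − 1) to *k*. The first two are cycles 1 to min(2, *k*). Infusions after the first two number max(0, *k* − 2).

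| *k* | Last two | Infusions after the last two | First two | Infusions after the first two |
|---|---|---|---|---|
| 1 | {1} | 0 | {1} | 0 |
| 2 | {1, 2} | 0 | {1, 2} | 0 |
| 3 | {2, 3} | 0 | {1, 2} | 1 |
| 4 | {3, 4} | 0 | {1, 2} | 2 |

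As written, the lighter rule applies to nothing for any *k*. At *k* = 4, Cycles 1 and 2 fall under neither sentence. With *first two*, every infusion falls under exactly one rule.

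**Step 2: can a site apply the rule on the day?** Cycle *c* is one of the last two only if *k* ≤ *c* + 1.

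- Cycle 1 needs *k* ≤ 2. This depends on later stopping.
- Cycle 2 needs *k* ≤ 3. This also depends on later stopping, and the imaging that informs the decision is done before Cycle 3.
- Cycle 3 needs *k* ≤ 4. This is always true.
- Cycle 4 needs *k* ≤ 5. This is always true.

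The status is therefore always settled before dosing for 2 of the 4 cycles and not for the other 2, which are the first exposures. With *first two*, all four are known in advance.

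**Step 3: does a looser reading help?** Suppose subsequent is taken to mean any other infusion. Cycles 1 and 2 of a four-cycle patient then fall under the lighter rule, with readings during and after infusion only when clinically indicated. The first exposures still lose the mandatory readings.

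**Step 4: does another section supply the readings?** Section 5.3.3.1 lists the vital signs to be measured but does not time them around the infusion. The schedule marks vital signs at every cycle, but section 5.3.5 places Day 1 evaluations before the infusion unless otherwise noted, and footnote C is where the exception would be noted. Footnote K requires observation in an equipped area but does not mention vital signs.

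**Step 5: footnotes C and K side by side.**

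| | Closer rule | Lighter rule |
|---|---|---|
| Footnote C, vital signs after infusion | 1 hour, last two infusions | 30 minutes if clinically indicated, subsequent infusions |
| Footnote K, observation after infusion | at least 60 minutes, Cycles 1 and 2 | at least 30 minutes, from Cycle 3 |

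The times match; only the cycles differ. Replacing *last* with *first* in C makes the two footnotes agree cycle by cycle. K is not contradicted as the text stands, because its minimum observation times can be met alongside C. It serves here as evidence of intent.

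**The case against.** The strongest reply is that this is a translation slip and not a flaw in the plan. The English text is visibly mistranslated in many places, including the drug names. The sentence at issue is itself scrambled, with a stray *first* in the sentence that seems to need it. All the listed centres are Chinese hospitals, so whether any site worked from this English wording cannot be shown. A reader holding both footnotes would probably recover the intended meaning from K. It can also be said that the two sentences do not strictly conflict: the first can be followed and the second is merely empty.

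Much of this stands. A translation slip is the likely cause, no harm at the bedside is demonstrated, and the difficulty of knowing the last two in advance follows from the same wording and is not a second defect. Even on the literal reading the protocol keeps vital signs before each dose, a first infusion of at least 60 minutes, 60 minutes of equipped observation after Cycles 1 and 2, advice to patients about delayed symptoms, and recording of all adverse events.

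It does not remove the point. The wording stands in the current protocol, in an instruction that staff are meant to carry out. Calling the second sentence empty concedes that the footnote does not work as a pair of rules. K lets a reader infer the intended cycles, but it requires no recorded vital signs and so cannot stand in for C.

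**Conclusion.** Footnote C is wrong as written, and the correction is minor. Its lighter rule covers 0 infusions for any number of cycles from 1 to 4. Taken literally, 2 of the 4 infusions in a four-cycle patient carry no mandatory readings during or after infusion, and those two are the first exposures. No trial-wide count is claimed, because the number of cycles each patient will receive is not known.

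That the wording is defective follows from the text alone. That *first two* was meant is an inference, strongly supported by the matching split in footnote K but not confirmed against the source-language protocol. The practical effect is limited to how infusion safety monitoring is carried out and recorded. Nothing in the pCR endpoint, the two-stage design, the sample size or the error rates depends on it.

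**What to change.** Check the source-language protocol. If it confirms the inference, amend footnote C so that the closer vital-sign rule applies to the first two infusions (Cycles 1 and 2), and state that subsequent infusions means Cycle 3 onward. The 1-hour and 30-minute readings then line up with the 60- and 30-minute observation periods in footnote K, and each infusion's rule is known before dosing.

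The cost is a few words in one table footnote. The number of mandatory reading sets per patient is min(2, *k*) under either wording, that is 1, 2, 2 and 2 for *k* = 1, 2, 3 and 4. Only the cycles on which they fall change.

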5.4 Statistical analysis

5.4.1 Sample size and calculation basis

The historical control pCR rate was assumed to be 10% based on recent clinical studies. The expected pCR estimate for this study was 25%, representing a clinically significant improvement. The resulting zero and alternative assumptions are as follows:

The original assumptions to be tested were: h_0 : PCR rate = 25%

Corresponding alternative hypothesis: h_a : pcr rate > 25%

The Simon Phase II (Simon, 1989) design will be used to test the superiority of the combination

of neoadjuvant therapy with Ampley monoclonal antibody as compared with the historical control. The expected Class I error rate for the project (ineffective study drug but effective promotion) $\alpha=0.05$, with 80% confidence. An interim efficacy and safety analysis will be performed when 18 subjects are enrolled. Of the 18 subjects in the first phase, the second phase was not performed if < 2 effective cases of complete pathological response were achieved. If there were ≥ 2 valid cases in Phase 1, continue with Phase 2 until there are a total of 43 subjects. If the total effective cases in the first and second stages were not less than 7, it could be determined that the pCR of the new adjuvant therapy in this study was significantly improved compared with the historical control, thereby demonstrating the superiority and efficacy of the new adjuvant therapy in this study. A 10% dropout rate was considered for this study, which required the recruitment of a total of 48 subjects. The statistical design was calculated using an online statistical tool approved by the Design Department of Sun Yat-sen Memorial Hospital, Sun Yat-sen University (<http://cancer.unc.edu/biostatistics/program/ivanova/simonstwostageDesign.aspx>) (Ivanova & Deal, 2016).

5.4.2 data analysis set

Safety analysis set: Includes all patients who received at least 1 dose of any study drug (any component of neoadjuvant combination therapy).

Efficacy analysis set: Includes all patients who received at least 1 dose of any study drug treatment (any component of neoadjuvant combination therapy) followed by radical cystectomy.

5.6.3 Statistical analysis plan.

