Clinical Study Protocol

Protocol Name: A Clinical Study of Disitamab Vedotin for Injection Combined With Penpulimab Injection in Neoadjuvant Therapy for Patients With HER2-expressing Cisplatin-intolerant cT2-T4aNxM0 Bladder Urothelial Carcinoma

Sponsor: Sun Yat-sen Memorial Hospital, Sun Yat-sen University

Version number: V1.0

Version date: 2022.5.1

Signature confirmation of scheme:

Compliance Statement

In compliance with the Provisions of the Good Laboratory Practice Regulations, Administrative Measures for Investigator-initiated Clinical Studies in Medical and Health Institutions (for Trial Implementation) and the Declaration of Helsinki, participants pledged to conduct this study in accordance with this protocol. Participants must be trained to conduct the study after obtaining the written approval of the Ethics Committee and the informed consent of the subjects. Protocol modifications need to be re-approved.

I. programme summary

Project Name: A Clinical Study of Disitamab Vedotin for Injection Combined With Penpulimab Injection in Neoadjuvant Therapy for Patients With HER2-expressing Cisplatin-intolerant cT2-T4aNxM0 Bladder Urothelial Carcinoma

Abbreviation of Scheme: RC48-C039

Test purpose:
 
To evaluate the efficacy and safety of neoadjuvant treatment with Disitamab Vedotin for Injection Combined With Penpulimab Injection in patients with cT2-T4aNxM0 bladder urothelial carcinoma and HER2-expressing cisplatin intolerance.

Test brief:
 
The single-armed, exploratory clinical study of vidicon monoclonal antibody combined with pie Ampley monoclonal antibody designed for cisplatin-intolerant patients with cT2-T4aNxM0 bladder urothelial carcinoma in this study confirmed the effectiveness and safety of the new adjuvant treatment of vidicon monoclonal antibody combined with pie Ampley monoclonal antibody for cisplatin-intolerant patients with cT2-T4aNxM0 bladder urothelial carcinoma, and finally provided new evidence-based evidence for new adjuvant treatment of such patients.

Sample size:
 
This is a prospective clinical study. It is intended to collect 48 patients with cT2-T4aNxM0 bladder urothelial cancer who are HER2-expressing and cisplatin-intolerant, and all of them have received neoadjuvant treatment with vidicon monoclonal antibody in combination with pie Ampley monoclonal antibody.

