In recent years, immune checkpoint inhibitors (ICIs) have become a new option for the treatment of bladder cancer. A study of 114 patients with MIBC(T2-4aN0M0) showed that a complete pathological response rate (CRR) of 37% was achieved with three courses of neoadjuvant immunotherapy with 200 mg Pembrolizumab before radical resection [3-4]. A one-arm second-stage clinical trial included 95 patients with MIBC who received two cycles of Atezolizumab before radical resection. About 31% of the patients experienced complete pathological reaction during radical resection. The pathological stage of more than half of the patients was reduced to NMIBC, and the one-year recurrence-free survival rate (RFS) was 79% [5]. The above studies have demonstrated that neoadjuvant immunotherapy based on ICIs is a therapeutic option for patients with MIBC, especially those who are intolerant to chemotherapy. Studies have confirmed that after tumor resection, neoadjuvant immunotherapy will continue to trigger a stronger immune response mainly by CD8+ T lymphocytes, leading to longer survival time for patients [6]. In addition, the surgical safety of radical resection after neoadjuvant immunotherapy is not significantly different from other methods [7]. Although ICIs can benefit more patients with MIBC than neoadjuvant chemotherapy, the use of ICIs still faces many challenges. First, there are currently no biomarkers that can predict the sensitivity of patients with MIBC to new ICIs-based adjuvant immunotherapy. The guidelines point out that PD- L1 expression and tumor mutation burden may predict the pathological response of ICIs treatment in some patients, but it is still not recommended as the basis of treatment selection [8]. Second, some patients lose the opportunity of radical surgery due to adverse events caused by ICIs treatment [9]. Finally, there is still controversy over whether ICIs alone or in combination with other immune and chemotherapy regimens is optimal.

A C014 study published on ASCO 2021 showed excellent anti-tumor activity with the combination of vidicon and tripril monoclonal antibody, with a therapeutic ORR of 94.1% in 17 evaluable patients. The ORR of the combination regimen was also 100% in 10 new patients. Further

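### Success is worded as demonstrating superiority, but the rule tests only an unsourced 10% historical pCR, while the only neoadjuvant pCR rates the protocol reports are about 31% and 37%

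*Protocol*

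**What the plan says.** Section 5.4.1 of the protocol fixes the benchmark, the target and the conclusion.

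- Benchmark: "The historical control pCR rate was assumed to be 10% based on recent clinical studies". No study is named or referenced.
- Target: "The expected pCR estimate for this study was 25%, representing a clinically significant improvement".
- Printed null: "The original assumptions to be tested were: h_0 : PCR rate = 25" (per cent). This conflicts with the 10% benchmark two lines above it.
- Rule: a Simon two-stage design with 18 patients in stage 1, going on if there are at least 2 pCRs, and success at 7 or more pCRs among 43.
- Conclusion on success: pCR is significantly improved against the historical control, "thereby demonstrating the superiority and efficacy of the new adjuvant therapy in this study".

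Section 2.1 reports two neoadjuvant pCR rates. For pembrolizumab alone: "A study of 114 patients with MIBC(T2-4aN0M0) showed that a complete pathological response rate (CRR) of 37% was achieved with three courses". For atezolizumab alone, in 95 patients: "About 31% of the patients experienced complete pathological reaction during radical resection". The same section presents checkpoint inhibitors as an option particularly for patients who cannot tolerate chemotherapy.

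The programme summary describes the trial as "The single-armed, exploratory clinical study of vidicon monoclonal antibody", and section 2.1 says that it should guide a later Phase III trial.

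**The concern.** The benchmark is credited to recent studies, but nothing in the protocol yields 10%. The recent neoadjuvant studies it does cite gave roughly three times that rate or more, with one checkpoint inhibitor. The trial regimen combines a PD-1 antibody with an antibody-drug conjugate, yet its target of 25% is below both cited figures.

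A test against 10% answers a narrow question: is the pCR rate above 10%? The concluding clause turns the answer into a general statement of superiority and efficacy, in a single-arm study that the protocol itself calls exploratory. A report could follow that wording faithfully and label a result superior although it falls below every neoadjuvant rate in the protocol's own background. A team planning the Phase III trial could then take more from the label than the test supports.

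**Working it through.** **Inputs.** From section 5.4.1: p0 = 10%, p1 = 25%, alpha 0.05, 80% (printed as confidence, read here as power), n1 = 18, n = 43, 10% dropout. From the programme summary: tests are one-sided and intervals are one-sided 95% unless otherwise specified. From section 2.1: 31% and 37%.

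**1. Reproduce the plan's figures.** An exact binomial search for the Simon optimal design with p0 = 0.10, p1 = 0.25, one-sided alpha 0.05 and power 0.80 gives n1 = 18 and n = 43. The trial goes on with at least 3/18 and succeeds with at least 8/43. Exact alpha is 0.048 and power is 0.800. Dropout: 43 / 0.9 = 47.8, rounded up to 48. So 18, 43 and 48 all reproduce, and 10% is the null that was actually used. The printed null of 25% is a misprint.

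**2. The printed cut-offs.** In Simon's notation r1 = 2 and r = 7 are the largest counts that still fail. The protocol uses 2 and 7 as the smallest counts that pass, so each cut-off is one too low. The probability of success is

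P(success | p) = Σ over x ≥ g1 of Bin(x; 18, p) × P(Y ≥ g − x), with Y ~ Bin(25, p),

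where g1 is the count needed to go on and g the total needed to succeed.

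| True pCR | Printed rule (2/18, 7/43) | Simon optimal (3/18, 8/43) |
|---|---|---|
| 10% | 0.122 | 0.048 |
| 20% | 0.749 | 0.565 |
| 25% | 0.915 | 0.800 |
| 31% | 0.982 | 0.937 |

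At a true rate of 10% the printed rule has type I error 0.122, not 0.05.

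**3. Lowest results that would be called superior** (Clopper-Pearson, two-sided 95%).

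- Printed rule: 7/43 = 16.3%, CI 6.8% to 30.7%.
- Simon optimal rule: 8/43 = 18.6%, CI 8.4% to 33.4%.

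Since 13/43 = 30.2% and 14/43 = 32.6%, every success from 7/43 to 13/43 (or from 8/43 under the Simon rule) is below 31%. Since 15/43 = 34.9% and 16/43 = 37.2%, every success up to 15/43 is below 37%.

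**4. How often this would happen.** If the true pCR equals the 25% target, the probability of a success with an observed rate below 31% is 0.750 under the printed rule and 0.636 under the Simon rule.

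**5. What exceeding the cited rates would take.** This treats 31% and 37% as fixed numbers and uses single-stage exact limits at n = 43.

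| Lower limit above | One-sided 95% (protocol convention) | Two-sided 95% |
|---|---|---|
| 31% | 19/43 (lower limit 31.2%) | 20/43 (31.2%) |
| 37% | 22/43 (37.7%) | 23/43 (37.7%) |

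These counts are far above 7 or 8.

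**The case against.** Four points on the other side deserve weight.

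**The comparator is stated.** Section 5.4.1 sets up the test against the historical control and ties the improvement to that control. A reader might infer that the protocol will claim superiority over checkpoint inhibitor monotherapy, or a benefit from adding the antibody-drug conjugate. It makes neither claim. This stands. What remains is that the concluding clause speaks of superiority and efficacy in general terms, and that the control behind it is never identified.

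**The cited cohorts may not be the right benchmark.** Section 2.1 describes the 37% cohort as T2-4aN0M0 and the 31% cohort only as MIBC. Neither is described as cisplatin-intolerant or HER2-expressing, whereas this trial enrols cNx, HER2-expressing, cisplatin-intolerant patients. The cited studies' pCR definitions and denominators are not given. A reader might therefore go too far in concluding that the null ought to be 31% or 37%; the documents do not establish that. A low reference rate for an exploratory study is a defensible choice, but the protocol gives no reason for this one, and the basis it names does not match the studies it cites.

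**The starkest figure depends on a separate error.** It is tempting to say that superiority could be declared with an interval wholly below 31%. That is true only at 7/43. At the correct cut-off of 8/43 the interval reaches 33.4% and includes 31%, so the argument should not rest on it.

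**Presentation of intervals can be left to the SAP or the report.** That is fair for layout. The null, its stated basis and the wording of the conclusion, however, are fixed in the protocol.

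**Conclusion.** The point holds as a fault in the stated basis for the 10% and in the wording of the conclusion. It does not show that the sample size or the choice of a 10% null is wrong.

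Its size, with the cut-offs corrected: the lowest success is 18.6%, and successes from 8/43 to 13/43 (18.6% to 30.2%) lie below both neoadjuvant rates the protocol reports. A regimen with a true pCR of 31% passes with probability 0.94, so passing says little about performance relative to 31%. Under the printed cut-offs the lowest success is 16.3%. Even the narrow statement that pCR exceeds 10% is then not supported at alpha 0.05, because the type I error is 0.122.

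This rests on reading 80% confidence as power, on 43 evaluable patients, and on treating 31% and 37% as context and not as established comparators for this population.

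**What to change.** Keep the sample size and the 10% null, and change the following.

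1. State in section 5.4.1 what the 10% represents and cite its source. Say why the 31% and 37% cohorts are or are not comparable with this population.
2. Correct the printed hypotheses so that the null is 10%. Correct the cut-offs to at least 3/18 and at least 8/43, so that the test holds alpha 0.05 against 10%. Section 5.2.6 repeats the stage 1 rule and must be brought into line.
3. Reword the conclusion on success as a pCR rate above the 10% historical benchmark, in place of superiority and efficacy.
4. Report the exact confidence interval beside the cited 31% and 37% as context. State that success does not imply superiority over checkpoint inhibitor monotherapy. If a comparison is made, the counts in step 5 of the working show what a lower limit above those rates would need.

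One detail for item 4: at 8/43 the ordinary one-sided 95% exact lower limit is 9.6%, just under 10%, although the two-stage test rejects with alpha 0.048. The ordinary interval ignores the stage 1 stopping rule. The plan should say that the decision follows the two-stage rule, or use an interval that allows for the two stages.

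The cost is an amendment to the wording and cut-offs and a less favourable claim. At the 25% target, power falls from 0.915 under the printed rule to 0.800, which is the intended value. No extra patients are needed.
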